5 STUDY POPULATION

5.1 INCLUSION CRITERIA

In order to be eligible to participate in this study, an individual must meet all of the following criteria:

1. Provision of informed consent (adult participant), or consent of parent/legal guardian in conjunction with adolescent assent (minor participant)
2. 13 to 18 years of age
3. Endorses dance as their primary sport, or participates 3 days per week or greater in dance prior to injury
4. Stated willingness to comply with all study procedures including the intervention regimen and availability for the duration of the study
5. Access to a device with which the SuperBetter app can be downloaded and used

5.2 EXCLUSION CRITERIA

An individual who meets any of the following criteria will be excluded from participation in this study:

1. Dance is not a primary sport or less than 3 days per week spent dancing prior to injury (skater, gymnast, other sport)
2. Requiring surgery or prior surgery for the injury being treated
3. Injury outside of the leg below the knee
4. Known eating disorder or bone density issue (documented abnormal Z score and/or eating disorder diagnosis upon review of the medical chart)
5. Verbalized plans to not return to dance after recovery from the injury

5.3 LIFESTYLE CONSIDERATIONS

Not applicable.

5.4 SCREEN FAILURES

Potential subjects will not be consented for this study unless they meet all of the inclusion criteria. Subjects that are enrolled in the study but are later determined to meet exclusion criteria will be considered screen failures and will be removed from the study and the reason for their removal will be documented.

6 STUDY INTERVENTION

6.1 STUDY INTERVENTION(S) ADMINISTRATION

6.1.1 STUDY INTERVENTION DESCRIPTION

The study intervention will be mental health exercises via the SuperBetter app for dancers participating in PT rehab for foot or ankle injuries. The control will be PT rehab only, without implementation of the SuperBetter app.

Subjects who enroll and are randomized into the treatment arm will be assisted in clinic to log into the app SuperBetter. They will be added to the group run by the “host”/study staff. The SuperBetter app offers a daily exercise on a schedule that will be managed by the “host” or study staff. Subject will complete 1 full activity per day. This activity will not exceed 15 minutes in total including app boot-up, but the full activity itself will not exceed 10. These activities ask participants to practice different exercises that might be found in Cognitive Behavioral Therapy, such as mindfulness. They are framed like a game for engagement, where the subject can “get a power up” when they take 30 seconds to breathe deeply and think of 3 loved ones, as an example. 1 full daily activity is constituted by 4 to 6 very brief activities similar to the previously described.

Both groups will undergo physical exams at their normally scheduled orthopedic appointments at baseline, 8 weeks, 3 months, 6 months, 12 months, 18 months, and 24 months where presence/absence of reinjury, return to dance, adherence to PT and/or the SuperBetter app, type(s) of dance, and hours of dance per week will be assessed. Both groups will be asked to complete the PROMIS, SCS, and FAAM at baseline, 3-, 6-, 12-, 18-, and 24 months.

6.1.2 DOSING AND ADMINISTRATION

All subjects will receive an initial PT order for 8 weeks. The treating physician may order an additional 4 weeks of PT depending on the individual patient and injury. Total number of attended PT appointments for each patient will be recorded. Subjects randomized into the treatment group will undergo mental health exercises 5 days per week, approximately 10 minutes per day, for 12 weeks alongside their 8 or 12 weeks of normally scheduled PT appointments. They will practice these exercises on a mobile device via the SuperBetter app. Those randomized into the control group will also participate in a physical therapy treatment program for 8 weeks or 12 weeks with no utilization of the SuperBetter app.

6.2 PREPARATION/HANDLING/STORAGE/ACCOUNTABILITY

Leave blank. Text should be included under the relevant subheadings below.

6.2.1 ACQUISITION AND ACCOUNTABILITY

Not applicable, as our project utilizes a mobile app rather than a physical product or device. It will be readily accessible by downloading from the app store.

6.2.2 FORMULATION, APPEARANCE, PACKAGING, AND LABELING

Not applicable.

6.2.3 PRODUCT STORAGE AND STABILITY

Not applicable.

6.2.4 PREPARATION

Study staff will assist in downloading and accessing the SuperBetter app for those patients in the treatment arm. The application goes through an introductory training with the participant prior to completing their first exercise. This introductory training will consist of instructions for using the app and will be done at the participant's home.

6.3 MEASURES TO MINIMIZE BIAS: RANDOMIZATION AND BLINDING

Patients who meet inclusion criteria at this single site will be offered enrollment in this RCT. Enrolled patients will be randomized into one of 2 groups. It will be true randomization without patient preference but will not be blinded. There are no sub-studies or stratifications to be performed within this group.

6.4 STUDY INTERVENTION COMPLIANCE

Email reminders will be sent through the app by the study team to remind the subject to complete their exercise(s). Subjects in the study group will be asked if they have been participating in the app usage and/or PT exercises prescribed at their clinic visits. The study staff will serve as a "host," and new treatment arm participants will be added to a group that is managed by the "host"/study staff. The host account has the capability to see whether a participant has completed daily exercise(s) or not. Noncompliance will be determined as a subject not registering in the app, or not using the app at all. If a subject is using the app less than prescribed, they will still be included but we will make note of their number of activities completed and will verbally inquire about their app usage at their following clinic visit.

6.5 CONCOMITANT THERAPY

Not applicable.

6.5.1 RESCUE MEDICINE

Not applicable.

7 STUDY INTERVENTION DISCONTINUATION AND PARTICIPANT DISCONTINUATION/WITHDRAWAL

7.1 DISCONTINUATION OF STUDY INTERVENTION

Discontinuation from the SuperBetter exercises does not mean discontinuation from the study, and remaining study procedures should be completed as indicated by the study protocol. If a clinically significant finding is identified (including, but not limited to changes from baseline) after enrollment, the investigator or qualified designee will determine if any change in participant management is needed. Any new clinically relevant finding will be reported as an adverse event (AE).

The data to be collected at the time of study intervention discontinuation will include the following:

- Clinical exam
- Outcomes (FAAM, PROMIS, SCS)
- Type of dance
- Hours of dance per week
- Number of PT sessions completed
- Duration of time in PT from start to finish
- Type of injury
- Amount of PT done prior to enrollment
- Repeat and new injuries
- Full return to dance (only if discontinuing past 12 weeks)
- Persistent pain with dance (only if discontinuing past 12 weeks)
- Additional treatment

7.2 PARTICIPANT DISCONTINUATION/WITHDRAWAL FROM THE STUDY

Participants are free to withdraw from participation in the study at any time upon request.

An investigator may discontinue or withdraw a participant from the study for the following reasons:

- Failure to follow up
- Change of mind regarding randomization
- Significant study intervention non-compliance, defined as not registering in or using the app once
- If any clinical adverse event (AE), laboratory abnormality, or other medical condition or situation occurs such that continued participation in the study would not be in the best interest of the participant
- Disease progression which requires discontinuation of the study intervention
- If the participant meets an exclusion criterion (either newly developed or not previously recognized) that precludes further study participation

The reason for participant discontinuation or withdrawal from the study will be recorded on the enrollment log. Research participants who sign the informed consent form and are randomized or are not randomized will be replaced.

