1 PROTOCOL SUMMARY

1.1 SYNOPSIS

Title:	Dance – Randomized Controlled Trial
Study Description:	This project aims to enhance self-compassion in adolescent dancers recovering from a foot and ankle injury by incorporating the use of a mental health intervention app using gamified design during their recovery.
Objectives:	Primary Objective: To assess rates of return to dance without limitations after start of non-operative treatment in dancers recovering from foot and ankle injuries Secondary Objectives: 1) To assess self-compassion in the recovering dancer during and after the nonoperative treatment of their foot and ankle injury 2) To assess musculoskeletal function during and after the recovery process
Endpoints:	Primary Endpoint: Return to dance after treatment of injury Secondary Endpoints: 1) Self Compassion (SCS) scores collected at 3, 6, 12, 18, and 24 months 2) Foot and Ankle Ability Measure (FAAM) and Patient-Reported Outcome Measurement Information System (PROMIS)
Study Population:	13-18 year old dancers
Phase:	Not applicable – not a drug trial
Description of Sites/Facilities Enrolling Participants:	Rady Children's Hospital, San Diego
Description of Study Intervention:	Qualifying participants will all be placed in a physical therapy recovery program for their injury and randomized into treatment or control group for implementation of the gamification mental health app to use during their recovery path. Outcomes scores for pain, physical function and emotional distress will be collected at the time of enrollment, 3 months, 6 months, 12 months, 18 months and 24 months after the start of treatment.
Study Duration:	4 years
Participant Duration:	2 years

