4 STUDY DESIGN

4.1 OVERALL DESIGN

Null hypothesis (H_0): There will be no difference in self compassion scores to return to unrestricted dance at 3 months between the mental health app group and control group.

Alternative hypothesis (H_1): Self compassion and return to unrestricted dance is expected to be improved in the mental health app treatment group compared to control group.

Patient Enrollment and Randomization: Patients who meet inclusion criteria at this single site will be offered enrollment in this RCT. Enrolled patients will be randomized into one of 2 groups. It will be true randomization without patient preference but will not be blinded. There are no sub-studies or stratifications to be performed within this group.

Trial Interventions: Following randomization, the control group will undergo physical therapy treatment only while the experimental group will also participate in mental health exercises through the app, SuperBetter, for approximately 10 minutes 5 days per week for 12 weeks. All participants will have a minimum order of 8 weeks of physical therapy. At 8 weeks, depending on the individual patient and injury, the doctor may order an additional 4 weeks of PT, for a total of 12. This will be according to the physician's standard of care for their practice and clinical expertise. The number of PT visits ultimately attended by each subject will be recorded. If those in the treatment arm are not prescribed 4 additional weeks of PT at the 8-week time period, they will still use the app for 4 additional weeks for a total of 12 weeks of app usage.

Data collection: All patients in both groups will return to clinic at 3 months, 6 months, 12 months, 18 months, and 24 months. The 24-month visit represents completion of participation in the study. Throughout the trial, patients will be monitored for safe usage and engagement with the mobile app, to determine if they need to stop or limit the intervention.

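### Section 7.2 lets an investigator withdraw a dancer from the study because progression requires stopping the intervention, although 7.1 keeps such dancers in follow-up; her 12-month primary outcome would probably be lost

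*Protocol*

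**What the plan says.** Protocol 7.1 deals with stopping the intervention: "Discontinuation from the SuperBetter exercises does not mean discontinuation from the study, and remaining study procedures should be completed". Protocol 7.2 deals with leaving the study. Its list of reasons for which an investigator may withdraw a participant includes "Disease progression which requires discontinuation of the study intervention". The same list has separate grounds for a medical situation that makes continued participation against the participant's interest, and for an exclusion criterion that develops or comes to light later.

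Section 6.1.1 identifies the study intervention as the app exercises and adds: "The control will be PT rehab only, without implementation of the SuperBetter app". PT is given to both arms and is described beside the app in the synopsis ("Qualifying participants will all be placed in a physical therapy recovery program for their injury"), in 4.1 ("All participants will have a minimum order of 8 weeks of physical therapy") and in 6.1.2 ("All subjects will receive an initial PT order for 8 weeks").

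The data listed in 7.1 for collection at discontinuation include "Full return to dance (only if discontinuing past 12 weeks"). Section 7.2 also says: "Research participants who sign the informed consent form and are randomized or are not randomized will be replaced".

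Sections 9.1 and 9.2 set the primary comparison, return to unrestricted dance, at 12 months. Section 9.3 defines the intention-to-treat set as everyone who starts treatment, but 9.4.2 excludes subjects with no primary outcome. Section 9.2 refers to 9.4.2 and 9.4.3 for sensitivity analyses; those two sections state only exclusions.

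**The concern.** The trigger in 7.2 is that the intervention has to stop. That is the event which, under 7.1, should leave follow-up intact. Where a dancer cannot safely continue, the other grounds in the list already apply. What this bullet adds is the dancer who must stop the intervention but could still be examined and asked whether she is dancing.

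If she is withdrawn, her 12-month status is likely to be missing and 9.4.2 leaves her out. The reason for the loss, a worsening injury, is closely tied to the outcome. The trial is unblinded and plans only 50 participants, so a few discretionary withdrawals concentrated in one arm could shift the comparison of return rates.

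**Working it through.** **Timing.** The app runs for 12 weeks (4.3) and PT for 8 or 12 weeks (6.1.2). A withdrawal that follows from stopping either one early comes well before month 12. The discontinuation data do not fill the gap, because return to dance is recorded at that point only after week 12. I take 12 months as the endpoint, as in 9.1 and 9.2. The null hypothesis mentions 3 months; on that reading the outcome could still be missed, for the same reason.

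**The plan's own figures.** The plan gives no number for this ground. Its nearest figure is 19 per group for 60% versus 95%, which the unpooled normal approximation reproduces: (1.96 + 0.842)² × (0.60 × 0.40 + 0.95 × 0.05) / 0.35² = 18.4, rounded up to 19. The point does not depend on it.

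**Inputs for the illustration.**
- From 9.2: 50 participants and a 60% return rate in the control arm.
- Assumed: 1:1 allocation, so 25 per arm; no true effect, so 15/25 = 60% in each arm; k dancers withdrawn before month 12 and excluded; each with chance q of having returned by month 12.

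**App arm only, excluded.** App rate = (15 − kq)/(25 − k), against 15/25 = 60% in control.
- q = 0: 15/24 = 62.5%, 15/23 = 65.2%, 15/22 = 68.2% for k = 1, 2, 3. Apparent advantage 2.5, 5.2 and 8.2 points.
- q = 0.3: 14.7/24 = 61.25%, 14.4/23 = 62.6%, 14.1/22 = 64.1%. Advantage 1.3, 2.6 and 4.1 points.
- q = 0.6: 60% for every k, so no bias.

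**App arm only, each replaced by a dancer with a 60% chance of return.** App rate = (15 − kq + 0.6k)/25.
- q = 0: 62.4%, 64.8%, 67.2%. Advantage 2.4, 4.8 and 7.2 points.
- q = 0.3: 61.2%, 62.4%, 63.6%. Advantage 1.2, 2.4 and 3.6 points.

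Replacement restores the count but hardly reduces the bias.

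**Both arms.** With equal k and q in each arm the difference is 0. With two withdrawn from the app arm and one from control at q = 0, it is 65.2% − 62.5% = 2.7 points.

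**Significance.** The largest of these null cases, 15/22 versus 15/25, gives a two-sided Fisher p of 0.76.

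**The case against.** The strongest objection is that the ground will seldom be used. Section 6.1.1 describes an activity of at most 10 minutes on a phone, and the documents describe no course of a foot or ankle injury that would require stopping it. Disease progression is not defined for an injury trial, and the bullet reads like general-purpose text. This stands, and it limits the size of the problem. The sentence is nevertheless operative.

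Next, 7.1 can be read as the default and 7.2 as a discretionary exception, since 7.2 says only that the investigator may withdraw. A reader might infer a flat contradiction; the text supports only a tension. It leaves the investigator without guidance on which section governs when the sole reason is that the intervention must stop.

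Several stronger readings are tempting, and the documents do not support them:
- *That the ground can remove dancers from the app arm only.* Section 6.1.1 points that way, but PT for both arms is described alongside the app elsewhere, so this is not settled.
- *That the reference to discontinuing after 12 weeks shows PT to be part of the intervention.* App and PT both end by week 12, so the phrase favours neither reading.
- *That the 12-month status is certain to be lost.* Section 7.2 is silent on data after withdrawal and does not bar collection; return to dance is assessed at ordinary orthopedic appointments (6.1.1). Loss is likely, not certain.
- *That no analysis will offset the loss.* The sections cited in 9.2 describe no sensitivity analysis, but a statistical analysis plan that is not shown may do so.
- *That this could decide the trial.* One can pick counts where it does: 22/25 versus 15/25 gives Fisher p = 0.051, and removing one app-arm non-returner (22/24) gives p = 0.018. Those counts are chosen to sit at the threshold and say nothing about how likely this is.

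Finally, the exclusion rule in 9.4.2 acts on every missing outcome, and other grounds in 7.2, such as never using the app or a change of mind about randomization, may be used more often. That is fair. It is also true that moving this bullet alone would miss the most concrete form of progression, a dancer who comes to need surgery: she meets an exclusion criterion (5.2) and can be withdrawn on that ground. The fix has to cover her too.

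**Conclusion.** The point holds as a low-priority wording defect with a possible, unquantified bias. Section 7.2 permits, without requiring, withdrawal from the study for an event that 7.1 treats as no reason to end follow-up. Such a withdrawal would normally precede the primary endpoint, and 9.4.2 would then exclude the dancer if her outcome is missing.

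The direction depends on two things that the documents do not settle: whether the ground applies to one arm or both, and whether the withdrawn dancers are less likely to return. If it is used mainly in the app arm and they are, the bias favours the app, by 2.5 to 8.2 points for one to three certain non-returners under the stated assumptions. If it is used equally in both arms the bias largely cancels and only sample size is lost. The number affected may be zero.

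**What to change.** Move the progression bullet from 7.2 to 7.1, as a reason to stop the intervention only. Then add a sentence to 7.2 to this effect: after any investigator-initiated withdrawal, including for progression, best interest or a newly developed exclusion criterion such as surgery, return-to-dance status, reinjury and adverse events are still collected on the normal schedule in both arms unless consent is withdrawn, and questionnaires too where the participant accepts them. Section 5.4, which removes enrolled subjects later found to meet an exclusion criterion, should refer to the same sentence.

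Whether and when to stop the app or PT remains the investigator's decision. The cost is protocol wording, since the visits and forms already exist. The small downside is following a few participants who would otherwise have left.

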9.3 POPULATIONS FOR ANALYSES

- Intent-to-Treat (ITT): All participants who initiate treatment
- Per-Protocol (PP): Participants with full follow-up data and $\geq 80\%$ adherence to recovery protocol
- Safety Population: All participants (reporting adverse events and reinjury)
- Exploratory Subgroups: Participants may be stratified into tertiles or above/below median self-compassion for exploratory comparisons

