9.4.2 ANALYSIS OF THE PRIMARY EFFICACY ENDPOINT(S)

- The primary outcome of interest is return to dance (binary).
- The proportion of subjects in each group that returned to dance will be evaluated with Pearson's chi-square or Fisher's exact test depending on the distribution of outcomes. If there is fewer than 10 subjects in any group (control that returned to dance, control that did not return to dance, experimental group that returned to dance, experimental group that did not return to dance), Fisher's exact test will be used.
- Odds ratios will be calculated and presented for significant findings.
- Subjects will be excluded if they are missing data related to our primary outcome of interest.

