9.4.3 ANALYSIS OF THE SECONDARY ENDPOINT(S)

- Our secondary outcomes of interest are self-compassion scale (continuous), FAAM (continuous), PROMIS (continuous).
- Normally distributed data will be evaluated with ANOVA. Nonparametric data will be evaluated with the Mann-Whitney U.
- Subjects will be excluded from analysis if they are missing secondary outcomes of interest.

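### Section 7.2 lets unblinded investigators withdraw and replace randomised dancers for a newly arisen exclusion criterion that overlaps the primary endpoint, so non-returners can drop out of the primary analysis

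*Protocol*

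**What the plan says.** - **Withdrawal (7.2).** Among the reasons for which an investigator may withdraw a participant is "If the participant meets an exclusion criterion (either newly developed or not previously recognized) that precludes further study participation". The section adds: "Research participants who sign the informed consent form and are randomized or are not randomized will be replaced".
- **Exclusion criteria (5.2).** Two of them matter here: "Verbalized plans to not return to dance after recovery from the injury" and "Requiring surgery or prior surgery for the injury being treated".
- **Screen failures (5.4).** Enrolled subjects "later determined to meet exclusion criteria will be considered screen failures and will be removed from the study". The text does not say that the ineligibility must have existed at baseline.
- **Blinding (6.3).** There is none.
- **Analysis populations (9.3).** Intention-to-treat is defined as "All participants who initiate treatment", not as all randomised.
- **Missing outcomes.** Section 9.4.2: "Subjects will be excluded if they are missing data related to our primary outcome of interest". Section 9.4.3: "Subjects will be excluded from analysis if they are missing secondary outcomes of interest". Section 9.2 calls for available-case analysis and refers to 9.4.2 and 9.4.3 for sensitivity analyses. For missing data, those two sections contain only the exclusion rules just quoted.
- **Time point.** Section 9.2 sizes the trial on return to unrestricted dance at 12 months. The null hypothesis in 9.1 names 3 months.

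**The concern.** An exclusion criterion is harmless when applied before randomisation. Applied afterwards, it can select on outcome. A dancer who says after randomisation that she will not go back to dance has nearly declared a failure on the primary endpoint. One who comes to need surgery has a related problem, although she may still return. Under 7.2 either can be withdrawn by staff who know the arm. If this happens before the primary time point and status is not obtained, 9.4.2 drops her and 7.2 recruits someone else.

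Whether a participant is analysed can then depend on both outcome and arm. Removal concentrated in one arm can create a difference or hide a real one. Equal removal in both arms mainly costs power. A later analysis plan cannot recover outcomes that were never collected.

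**Working it through.** **Does another section close the gap?**
- Section 7.1 keeps participants who stop the app in follow-up. It concerns stopping the intervention, not withdrawal from the study.
- Section 7.3 governs contact attempts after missed visits, not withdrawal by the investigator.
- No section requires return-to-dance status after a 7.2 withdrawal or says how such a participant counts.

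**Inputs from section 9.2.** Control return 60%, app 95%, two-sided alpha 0.05, Fisher's exact test, 50 enrolled. I take this as 25 per arm, in line with the equal groups in 9.2.

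**The plan's own figure.** The unpooled normal approximation gives (1.960 + 0.842)² × (0.60×0.40 + 0.95×0.05) / 0.35² = 7.85 × 0.2875 / 0.1225 = 18.4, so 19 per group, as stated in 9.2. The concern does not depend on this figure.

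**Assumption.** Let f be the share of non-returners who are withdrawn with status missing. The protocol gives no value; I use 10%, 25% and 50%. With 60% return, an arm of 25 has 10 expected non-returners, so these shares mean about 1, 2.5 and 5 people.

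**Apparent return rate** among those left = p / [p + (1 − p)(1 − f)]. For p = 0.60 and f = 0.50: 0.60 / (0.60 + 0.40×0.50) = 0.75.

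**Rejection rates.** Each participant returns with probability p, is a retained non-returner with (1 − p)(1 − f), or is removed with (1 − p)f. All tables are enumerated exactly and Fisher's test is applied to those retained.

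| Share removed, f | 0 | 10% | 25% | 50% |
|---|---|---|---|---|
| (1) No effect, 60% in both arms, removal in app arm only: apparent app rate | 60% | 62.5% | 66.7% | 75.0% |
| (1) Type I error | 3.0% | 3.8% | 5.4% | 13.2% |
| (2) 60% vs 95%, same share in both arms: apparent gap (points) | 35 | 33 | 30 | 22 |
| (2) Power | 82% | 82% | 76% | 56% |
| (3) 60% vs 95%, removal in control arm only: power | 82% | 80% | 70% | 40% |

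**Replacement back to 25 per arm, f = 50%.** Newcomers are subject to the same removal, so the apparent rates persist. In (1), 60% vs 75% gives type I error 13.0%. In (2), 75% vs 97.4% gives power 49%. Replacement does not repair the problem.

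**One participant.** 15/25 vs 22/25 gives Fisher p = 0.051. Withdrawing one app-arm non-returner gives 15/25 vs 22/24, p = 0.018.

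**Should missing simply count as not returned?** The buffer in 9.2 implies up to (50 − 38)/50 = 24% missing. If that share is missing at random, available cases (19 vs 19, 60% vs 95%) have 68% power. Counting missing as failure gives rates of 0.76×0.60 = 45.6% and 0.76×0.95 = 72.2% in 25 vs 25, and power of 40%. It is therefore better kept as a sensitivity analysis.

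**The case against.** The strongest reply is that this chain is possible rather than prescribed.

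- **The clause is narrow.** It is permissive and applies only where the criterion precludes further participation. Nothing says that a change of plans, or surgery, prevents a dancer from attending visits. This narrows the route, but the judgement remains with unblinded staff and nothing rules it out.
- **Withdrawn is not the same as missing.** Status is assessed at every visit, so a dancer withdrawn at month 7 has 3- and 6-month data. If 3 months is the intended time point, much of the problem disappears. That is right, and the exposure is greatest under the 12-month endpoint used for sizing.
- **Section 7.1 lists full return to dance among data collected at discontinuation after 12 weeks.** It may have been meant for study exit too, but its heading limits it to the intervention. A status recorded at exit is also not the 12-month status.
- **Section 5.4 reads naturally as baseline ineligibility found late.** Agreed; it is supporting text only, because 7.2 says expressly that newly developed criteria count.
- **Replacement and the intention-to-treat wording do not cause the bias.** Largely true. Replacement hardly changes type I error (13.0% against 13.2%). The point is that neither rule brings the removed participants back.
- **The large figures need strong inputs.** At a 10% share the effect is small, the criteria are the same in both arms, and the single-participant example is a borderline case chosen for illustration. All true. One-sided removal is made possible by the open design, but nothing shows that it is expected.

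A tipping-point analysis would often be left to an analysis plan. Here, however, 9.2 says that the sensitivity analyses are in 9.4.2 and 9.4.3, and they are not.

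**Conclusion.** The concern holds and must be fixed. The stated rules allow primary-endpoint failures to leave the denominator after randomisation, by a discretionary decision made with the arm known, and no other section prevents it.

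The size rests on assumed removal shares and on how removal is split between arms; neither can be learned from the protocol, nor can the direction. The effect is slight at a 10% share. In the worst case examined, a 50% share in one arm only, type I error is 13.2% under no effect (app arm) or power falls to 40% (control arm). With 50 participants, a single withdrawal can change the conclusion.

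**What to change.** - **5.4 and 7.2.** State that only ineligibility that existed before randomisation, shown by pre-randomisation records, can remove a participant from the analysis. Participants who first meet an exclusion criterion later stay in follow-up for outcome status unless they themselves refuse, and are not replaced. They count in their assigned arm by observed dance status; one known to have given up dance counts as not returned.
- **9.3 and 9.4.2.** Define the primary analysis set as all randomised participants as assigned, apart from that documented pre-randomisation ineligibility.
- **9.4.2.** Write in the sensitivity analyses promised in 9.2 for status that is truly unknown: missing counted as not returned, and a tipping-point analysis. Use the 18- and 24-month visits to recover 12-month status where possible. Do not make missing-as-not-returned the primary rule: besides the power loss shown above, it could penalise the app arm alone, because 7.2 also allows withdrawal for never using the app.

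The cost is wording in four sections, outcome follow-up at visits already scheduled, and one sensitivity table. Observed return rates may be lower, by an amount that depends on how many would otherwise have been removed. Nothing here changes treatment or clinical care.
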